Treatment of mild cognitive impairment with transcutaneous vagal nerve stimulation

NCT03359902

6/30/2021

University of Florida IRB-01

Protocol

- 1. Title:** Treatment of mild cognitive impairment with transcutaneous vagal nerve stimulation
- 2. Investigators:** [name] PhD (PI), [name], [name], [name], [name]
- 3. Collaborators:** [name] (Statistician, works with deidentified data)

4. Abstract:

Patients with amnestic mild cognitive impairment (MCI) often have compromised quality of life. Cognitive impairment is a major contributor to decrements in quality of life and progression of MCI often leads to loss of independence and withdrawal from social participation. MCI, in many patients, is an early expression of neurodegenerative disease. Patients with MCI frequently convert to Alzheimer's disease (AD) (12-16 percent by some estimates per year). Treatments for MCI are of limited scope and availability and of limited effectiveness. Thus, there is great need for treatments that can improve cognition and extend quality of life in patients with MCI. Early intervention (prior to the development of dementia) is more likely to successfully treat this population. We propose to investigate the effect of a non-invasive and safe intervention that should have direct influence on brain systems underlying AD, transcutaneous vagal nerve stimulation (tVNS). This promising approach has not yet been studied in patients with MCI.

The hippocampus is a structure that deteriorates in AD. Further, studies have suggested that the locus coeruleus (LC), the brainstem nucleus that is the brain's sole source of norepinephrine (NE), may be one of the first structures that deteriorate in patients with AD. The release of NE in the hippocampus and frontal lobes has an important role in cognition and is critical in mediating memory and attention. The ascending portions of the vagus nerve form synapses within the nucleus of the solitary tract, which projects to the LC and to the hippocampus. The LC also projects directly to the hippocampus. Thus, vagal nerve stimulation (VNS) may ameliorate symptoms of MCI. We have demonstrated, in patients with epilepsy, that VNS improves memory; however, VNS has not been used to treat patients with MCI. VNS can now be performed without surgery by transcutaneous stimulation of the auricular branch with electrodes on the external ear. tVNS has the potential to improve cognition and may even alter the course of decline in patients with MCI. We will employ a multimodal MRI-based neuroimaging approach combined with comprehensive and targeted cognitive testing to assess changes with tVNS in cognition in patients with MCI.

We will evaluate the effects of tVNS on patients who have been diagnosed with MCI. To maximize statistical power, we will employ a cross-over design with tVNS and control stimulation conditions (stimulating an area on the external ear that does not have nerve endings that connect to the vagus). Very little in the way of mechanistic data or understanding of individual differences in response to tVNS in MCI/AD has been published. Thus, this is a necessary study to evaluate the potential utility of tVNS to enhance cognitive performance in patients with MCI. These data may serve as a platform for supporting the development of a clinical trial with this technology.

5. Background:

A1.1 Public health significance 1) The Alzheimer's Association predicts there will be >16 million Americans with AD by the year 2050. 2) AD associated cognitive impairment directly contributes to a decline in quality of life and is thus a major public health concern. 3) Interrupting brain deterioration early in the degenerative process to reduce future disability is a major target of intervention. 4) MCI can be caused by several processes including AD pathology⁴⁻⁶. Because of heterogeneity and inconsistencies in the identification of MCI, estimates of prevalence and incidence vary. In a recent meta-analysis of people who are 55 years old or older, the prevalence percentage for patients with MCI in the US ranged from 18.8% - 28.3%⁷. Further, in patients with MCI, approximately 12%-16% convert to dementia each year. 5) Since MCI is associated with neuropsychiatric symptoms and functional decline⁸, MCI is associated with declines in quality of life⁹. 6) tVNS is a promising potential 1st line treatment with minimal side effects and multiple vectors of impact on systems that affect cognition including on primary areas of deterioration in MCI/AD. 7) Data from this study will provide mechanistic data on alterations in cognition induced by tVNS and will support the development of more extensive evaluation of this promising intervention.

A1.2 The locus coeruleus Studies of patients with AD have provided experimental evidence that the LC may be one of the earliest sites of AD pathology¹. Activation of the neurons of the LC modulates several processes that are altered in brains of patients at risk for AD including synaptic plasticity, inflammation, metabolism, and blood-brain-barrier permeability. Further, NE deficiency increases beta-amyloid deposition in the brain¹¹. Regardless of whether the LC deteriorates early, it projects to the hippocampus and, along with its role in NE production, may influence memory processes. Thus, enhancing LC function may be helpful in MCI.

A1.3 Mechanisms of cognitive dysfunction in MCI may be modifiable via tVNS About 30 years ago, it became possible to effectively stimulate the vagus nerve in humans. Vagal nerve stimulation (VNS) initially was used to treat patients with poorly controlled seizures¹². Because of its potential impact on hippocampal and prefrontal systems, VNS may impact memory encoding, retrieval, and working memory. See *figure 1*.

[figure not shown]

Figure 1. Simplified cognitive enhancement path for tVNS

A1.4 Methods of stimulating the vagus VNS is FDA approved, but requires surgical implantation of a device in the chest and electrodes placed around the vagal nerve in the neck. tVNS is a non-invasive and promising means of modifying brain function. tVNS stimulates the auricular branch of the vagus (located medially at entry of the acoustic meatus¹³). Because it does not directly stimulate descending cardiac fibers, it does not appear to affect mean heart rate or blood pressure and does not carry the cardiac risks of implanted VNS.

6. Specific Aims:

tVNS has the potential to improve cognition in patients with MCI and may even alter the course of decline. We will employ a multimodal approach including neuropsychological testing, structural and functional MRI to assess changes with tVNS in cognition in patients with MCI in support of the development of a therapeutic role for tVNS in the treatment of this disabling disorder.

Aim 1) Evaluate the influence of tVNS on memory performance in participants with MCI. tVNS may alter the activity of the areas of the brain that are critical for encoding or recalling memories and which are often impaired in patients with MCI. Therefore, tVNS may improve behaviors supported by these networks.

Hypothesis 1: During tVNS, participants with MCI will improve in verbal and visuo-spatial memory compared to off-tVNS performance (sham-stimulation).

Aim 2) Determine mechanisms of treatment response variability. Differences in the etiology and expression of MCI may result in different cognitive responses to tVNS. For example, patients with memory loss may have degeneration of the entorhinal cortex and hippocampus or injury to the frontal subcortical networks. These differences in neuroanatomical involvement produce different kinds of memory impairments. We will examine the relationships between the response to tVNS as a function of differences in baseline cognitive and structural presentation. *Further, in secondary analyses, we will examine the effects of biological variables such as sex and also common changes in the brain associated with aging including changes in healthy appearing white matter (DTI assessed) and white matter hyperintensities (leukoaraiosis as assessed through FLAIR MRI).*

Hypothesis 1: Those patients with amnestic MCI who have baseline memory impairment including flat learning curve, poor free recall, and reduced recognition memory will improve with tVNS treatment.

Hypothesis 2: Research has demonstrated that neurodegeneration of medial temporal structures is the best antecedent MRI marker of imminent conversion to AD, with decreased hippocampal volume (left > right) being the most robust. Since the hippocampus receives direct input from the NTS as well as norepinephrine from the LC, those participants with MRI evidence of degeneration of the hippocampus/entorhinal cortex (its direct path connections (using diffusion tensor imaging [DTI])) *will improve during tVNS and the degree of improvement may be related to the degree of atrophy.*

Hypothesis 3: Those patients with MCI who have baseline memory impairment including reduced working memory and poor retrieval with intact recognition will improve with tVNS.

Hypothesis 4: Since norepinephrine is important for the function of the prefrontal-executive systems, patients with deterioration of prefrontal cortex as evidenced by atrophy and/or white matter integrity loss will show improvements in retrieval and working memory with tVNS as assessed by cognitive testing (digit span, free retrieval memory after a delay) and *the degree of improvement may be related to the degree of structural abnormality.*

7. Research Plan: Experimental design The design of the study is a hybrid, crossover trial structure with randomized and counterbalanced order of tVNS or sham tVNS (to control for ability to detect stimulation/placebo effects) administration (see *table 1 for basic design elements*). This will allow us the benefits of both a parallel and crossover design in that we will have equal numbers of subjects who have received sham or tVNS at time point 1 allowing a between subject analysis, while also allowing a crossover analysis. This design also enables the assessment of potential carryover and practice effects. Participants will attend four contact periods: 1) consent, inclusion screening, MRI eligibility and screening, structured history interview; 2) MRI scan; 3) and 4) stimulus sessions separated by at least 7 days, each consisting of the experimental protocol described below.

Intervention	Predictor	Outcome
tVNS versus sham stimulation (counterbalanced)	Baseline/sham cognitive performance	Cognitive performance - Memory, executive function
	Hippocampal/entorhinal volume	
	White matter variables	

Table 1: Intervention, predictors, and outcomes

C2.1 Study participants will be patients who meet the diagnostic criteria for MCI (see 2.2 and 2.3 for criteria). In addition, we will recruit an additional group of healthy aged adults without MCI. All patients will have undergone neurological or neuropsychological evaluation. Participants will sign an informed consent or delayed consent prior to initiation of research activity. Each participant will also receive neuropsychological testing. To further improve our ability to identify mechanisms of memory change, we will also measure autonomic nervous system (ANS) activity and other measures of neuropsychological domains including executive functions and attention (see neuropsychological battery).

C2.2 Inclusion criteria The participants included in this study will be native speakers of English between the ages of 60-89. Potential MCI participants without an existing clinical diagnosis will perform a phone screen, potentially including the T-MMSE (if they verbally consent). The T-MMSE has high correspondence with the MMSE, a common first screening tool for clinicians. Participants who are not ruled out through the phone-screen and/or the T-MMSE will be invited for an intake interview. Intake criteria will be based on established NIA-AA/DSM-V criteria including patient/informant/clinician concern regarding a relative decline in cognition, and/or a global CDR of .5 with objective evidence of relative impairment in another domain that is based on neuropsychological testing for deficits²²⁻²⁴. To be included, participants will have a preservation of independence in functional abilities including performing activities of daily living and instrumental activities (i.e., not demented). Test performance will be judged as “impaired” if it is significantly (> or = 1.5SD) below the expected level (based on demographic information and educational level) based on normative data.

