Clinical and Health Psychology) that also evaluate patients that will meet our inclusion criteria. We may use certain UF services including I2B2 and Healthstreet.

Additionally, we will request a copy of the State of Florida Voter Registration registry. We will narrow down this list by voters that meet our age range (60-89) and send them an IRB approved flyer. This flyer would provide a brief overview of the study; as well as, study contact information for interested individuals.

C3.1 Procedural sequence The sequence and flow of the assessments to be conducted are as follows. Recruited participants will be screened over the phone after giving verbal consent. Participants will be mailed or emailed a map with directions to our study spaces if they request it. Participants who pass the initial phone screen will then be formally consented with a written ICF and then screened for inclusion/exclusion factors via interview, screening questionnaires, and review of medical records. Individuals who live farther away and are interested in the study but not wanting to make the drive without knowing they qualify for the study will have the option of having the intake administered by study staff at their (the potential participants) home. Any information and forms completed during this intake will be locked in a small filing cabinet and driven back to the University of Florida by study staff. All remaining study visits will be conducted at the University of Florida as usual.

Included participants will then undergo the MCI classification portion of the study, which characterizes the sample, collects covariates for mixed model analysis, and verifies group inclusion. Participants will be randomized between the two arms of the crossover sessions (initial tVNS vs. Sham). Behavioral portions of the testing will then be carried out twice, with at least one week between sessions (to avoid carryover effects). MRI scan will occur at least 72 hours from behavioral sessions.

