C5.1 MRI protocol We will use a research dedicated scanner in the UF Advanced MRI and Spectroscopy (AMRIS) facility. The scanning sequences will take ~1-1.5 hours to acquire and may include: 1) Structural MRI, 2) Diffusion Tensor Imaging (DTI). 3) fMRI 4) Magnetic Resonance Spectroscopy

Subjects will be provided a de-identified DVD with their structural scans if they request it. We will also mail copies of the DVD to subjects if they request it.

Task fMRI We will present the fMRI task (2-Back) using E-Prime software (Psychology Software Tools, Inc., Pittsburgh, PA) viewed through a double-mirror attached to the head coil. An MRI-compatible response box attached to the stimulus presentation computer will collect performance data.

2-Back. Verbal working memory will be assessed on a 2-Back and 0-back task, as in past studies^{19,47}. In both conditions, consonants are visually presented. In the 0-back condition, participants determine if each stimulus is the same or different from the previous stimuli, responding by binary button press. In the 2-back condition, participants respond yes if a stimulus is the same as the consonant two letters earlier, both the 0 and 2-back contain 33% targets. 8 blocks of both the 0-back and 2-Back conditions are pseudo-randomized across two 6-minute runs. Accuracy and reaction times are recorded.

C5.5 tVNS cognitive testing We will test the impact of tVNS with the following cognitive tests using:

- Repeatable Battery for the Assessment of Neuropsychological Status story learning and recall,
- Wechsler Memory Scale-IV Paired Associates I & II
- Phonemic and semantic fluency tests
- Paced auditory serial addition test (PASAT)
- WAIS-IV Digit Span (working memory) and Digit-symbol Coding ⁴⁸
- Rey Auditory Verbal Learning Test (RAVLT)
- ARCPT
- Trails
- tVNS or sham will be active throughout testing.

Possible Discomforts and Risks:

Non serious adverse events:

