Treatment of mild cognitive impairment with transcutaneous vagal nerve stimulation

NCT03359902

1/1/2018

C6.1 Data analytic strategy [name] (Co-I, biostatistician) will conduct the statistical analyses, which will be performed using statistical software, R or SAS. First, standard summary statistics will be provided for all measures (including behavioral and demographic [e.g., sex] measures, volumetrics from T1 weighted images, white matter integrity on DTI and white matter hyperintensities from FLAIR, and baseline neuropsychological test performance) by treatment (sham or active during the first stimulus session). Second, hypotheses will be tested with formal inferential techniques. Third, exploratory analysis for baseline neuropsychological test performance, brain regional volume, and other regional indices from DTI for predicting treatment response will be conducted. We will adjust for multiple comparisons by controlling the false discovery rate and determine statistical significance for each aim. The crossover design will increase the precision, where each subject serves as his or her own control and within subject comparison can be used. The increased power with greater precision to estimate the treatment differences reduces the necessary sample size. Despite this advantage, a potential problem in a crossover design is that carryover effects may bias the direct treatment effects. To account for the potential carryover effects, we will consider the following mixed-effect model. Let y_{ijk} denote the memory score measured at time period k from the j th subject in sequence i ,

$$y_{ijk} = \mu + \beta_{j(i)} + \gamma_k + \tau_{d(i,k)} + \lambda_{c(i,k)} + \epsilon_{ijk},$$

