where i =sequence (tVNS-sham or sham-tVNS), j =subject, k =period, μ is the overall mean, δ_i is the fixed effect of sequence i , $\beta_{j(i)}$ is the random effect for patient j with sequence i , γ_k is the effect of period k , $\tau_{d(i,k)}$ is the direct effect of the treatment applied during period k in sequence i , $\lambda_{c(i,k)}$ is the carryover effect of the treatment applied during period k in sequence i , and ϵ_{ijk} is the random error effect. Note that there is randomization of the subjects to the sequences. If the outcome measures do not follow a normal distribution, certain transformation, e.g., a Box-Cox transformation, will be applied before modeling. With this mixed-effect model, various hypotheses on the treatment effects, period effects and carryover effects can be separated and tested. If the carryover effect is not significant between the two sequences, then the data from two periods can be combined and analyzed. In the case that the carryover effect is significant, the overall conclusion about the treatment effect would be in question, however, the data from the first time period can still be used in testing for treatment effects because there would be no carryover from any previous applications of the treatments. Further, we will conduct secondary analysis for investigating the effect of tVNS on the other cognitive domains including language (phonemic and semantic fluency) and executive functions. To identify the factors that mediate the effects of tVNS, i.e., testing the hypothesis in Aim 2, the memory scores will be regressed on the selected factors, such as baseline memory performance (flat learning curve, poor free recall, reduced recognition memory; reduced working memory and poor retrieval with intact recognition), and hippocampal/entorhinal cortex volume (normalized by intracranial volume). Important covariates such as sex, age and education will be adjusted in the regression model if they relate significantly to the outcome variables. Variable selection can be conducted for the model under the standard Bayesian or frequentist framework. For example, a L1-penalty⁴⁹ might be used in variable selection under the frequentist framework. In addition to the plain linear regression model, the generalized additive model⁵⁰ will also be tried for the problem, which is expected to fit the data better and have a better power to detect the factors that are truly associated with the effects of tVNS.

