C6.2 Power and sample size considerations The enrollment sample of 60 participants is intended to provide data on the impact of tVNS on the cognitive performance in participants with MCI and predictors of improvement with treatment including brain volume changes associated with AD pathology. Further, these data will be used to indicate feasibility of a larger trial and to provide descriptive estimates of acute effects. To get a rough idea for the effectiveness of the trial, we made the following calculation. Assuming $\alpha = 0.05$, two-sided test, and 60 participants in total. If the carryover effect is negligible, we will have 90% power to detect an effect size of 0.604 for memory improvement in hypothesis 1 in aim 1 based on within subject comparisons. In the case that the carryover effect is significant and we use the first period data only (similar as in a parallel design), we will have 90% power to detect an effect size of $d=0.854$ for aim 1. For the regression analysis in predicting treatment response in aim 2), we will have 90% power to detect a factor that has a marginal correlation of $r=0.43$ with the response variable.

Overall, our methodology and analyses offer a comprehensive approach to understanding the mechanism of action of tVNS as a potential enhancer of cognition affected by decline in the continuum of AD. Our strategy should establish feasibility and our personalized medicine approach will allow us to interrogate treatment responsiveness and examine predictors of said responsiveness. Subsequent larger scale clinical trials including biomarkers such as amyloid imaging, CSF tau, and genetic subtypes (APOE) and longitudinal evaluation of sustainability of effects and whether decline in functional status can be achieved will follow.

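### Table 1 lets sham-session performance predict tVNS response, and the SAP does not fix the Aim 2 response; two readings that the text allows would give wrong answers

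*Protocol*

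**What the plan says.** Protocol section 7, Table 1, has "Baseline/sham cognitive performance" in its predictor column, beside hippocampal/entorhinal volume and white matter variables. Its outcome column gives cognitive performance. Aim 2 (Protocol section 6) asks how the response to tVNS varies with baseline cognition and brain structure, and does not mention sham performance as a predictor.

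SAP C6.1 first announces "exploratory analysis for baseline neuropsychological test performance, brain regional volume, and other regional indices from DTI for predicting treatment response". For the inference it then says that, in "testing the hypothesis in Aim 2, the memory scores will be regressed on the selected factors, such as baseline memory performance". It lists features of baseline memory (learning curve, free recall, recognition, working memory) but names no test and no visit. SAP C6.2 describes the same analysis as one of response: "For the regression analysis in predicting treatment response in aim 2), we will have 90% power to detect a factor" with a marginal correlation of 0.43 with the response variable. Response is not defined in either section. On multiplicity, C6.1 says: "We will adjust for multiple comparisons by controlling the false discovery rate and determine statistical significance for each aim".

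Two sets of cognitive scores are available. Protocol C3.1 places a classification stage before randomization that "collects covariates for mixed model analysis, and verifies group inclusion"; C2.4 puts the HVLT-R there. Protocol C5.5 lists the session battery, with different memory tests (RAVLT, paired associates, story recall), and states that "tVNS or sham will be active throughout testing". No administration of that battery without stimulation is described.

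**The concern.** Aim 2 is about who responds. In a crossover whose Aim 1 hypothesis measures improvement against sham, the natural response for each participant is the tVNS score minus the sham score. If the predictor is the sham score on the same test, that score enters both sides of the regression with opposite signs. A participant who happens to score low in the sham session then has a low predictor and a high apparent gain, so poorer performers seem to benefit more even when the true benefit is the same for all.

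The other route is to take the SAP sentence literally and regress the memory scores themselves. People who remember well at one visit remember well at another, so baseline memory will predict session memory whether or not tVNS does anything. That regression does not examine response.

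At stake is the responder profile that the study intends to pass on to larger trials. For the outcome tests, the only non-tVNS score that the documents describe is the sham score, so the first route is a realistic choice for an analyst who wants a same-test predictor.

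**Working it through.** **Inputs.** From SAP C6.2: n = 60, two-sided α = 0.05, 90% power at r = 0.43. Assumed, because the documents do not give it: the correlation ρ between a participant's sham and tVNS scores on one test, at 0.5, 0.7, 0.8, 0.9 and 0.95. Also assumed: equal variances and a constant tVNS effect, so there is no true moderation.

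**The plan's own figure.** By Fisher's z, power at r = 0.43 is Φ(atanh(0.43)·√57 − 1.960) = Φ(3.472 − 1.960) = 93.5%, not 90%. The detectable z is (1.960 + 1.282)/√57 = 0.429, which is r = 0.405 after back-transformation. The stated 0.43 therefore appears to be the untransformed z. It is slightly conservative and does not affect this point.

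**Reading (a): sham score S predicts T − S on the same test.** With unit variances, Cov(S, T − S) = ρ − 1 and Var(T − S) = 2(1 − ρ), so

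corr(S, T − S) = −(1 − ρ)/√(2(1 − ρ)) = −√((1 − ρ)/2).

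The simulation used 20,000 trials of 60 participants: S = a + e₁, T = a + e₂ + 0.3, Var(a) = ρ, Var(e) = 1 − ρ. The last three columns apply Benjamini–Hochberg at 5% to this predictor plus independent null predictors; the number of predictors is assumed.

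| ρ | Expected r | Rejects, one 5% test | FDR, 5 predictors | FDR, 10 | FDR, 20 |
|---|---|---|---|---|---|
| 0.5 | −0.50 | 98.7% | 94.7% | 91.6% | 87.8% |
| 0.7 | −0.39 | 87.5% | 70.9% | 62.0% | 53.1% |
| 0.8 | −0.32 | 70.3% | 47.1% | 37.6% | 29.5% |
| 0.9 | −0.22 | 41.2% | 19.9% | 14.2% | 9.9% |
| 0.95 | −0.16 | 22.4% | 8.8% | 5.6% | 3.5% |

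Solving √((1 − ρ)/2) = 0.43 gives ρ = 1 − 2(0.43)² = 0.63. Below that, the artefact alone is as large as the correlation in the power statement. Adding a 0.3 SD practice effect and a sequence term leaves the unadjusted rates at 98.5%, 87.3%, 69.5%, 40.2% and 22.2%.

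**Comparators for the same contrast.**
- Intake score with independent error: 4.7% to 5.2% unadjusted, and 0.4% to 0.5% with FDR over 10 predictors.
- A different test from the sham session: 4.9% to 5.1% if its errors are independent of the outcome test's. If they correlate 0.3, the rates over the five values of ρ are 21.1%, 14.0%, 10.6%, 7.9% and 6.5%.
- Mean of the two sessions: Cov((S + T)/2, T − S) = (Var T − Var S)/2, which is zero only under equal variances. Then it rejects 4.7% to 5.0%. At ρ = 0.7 with error SDs differing by 10%, 20% and 50%, it rejects 6.3%, 9.4% and 32.1%.

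**Reading (b): the memory score itself is the outcome.** With T regressed on S, the correlation and the slope both equal ρ; simulated mean slopes were 0.50 to 0.95. The test rejects in 98.6% of trials at ρ = 0.5 and in essentially all at 0.7 to 0.9. An intake score that correlates ρ with the session score gives 98.5% to 100%, so changing the predictor does not cure this reading. A slope below 1 here is not evidence of greater benefit in poorer performers.

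**The case against.** The strongest reply is that no sentence specifies the biased analysis. It needs a sham predictor, the same test on both sides and a difference-score response, and the SAP commits to none of the three. The intake reading is also the natural one: Protocol C3.1 has the classification stage collect covariates, C2.4 puts a memory test there, and SAP C6.1 summarises baseline test performance together with demographics and MRI measures. On that reading, with a tVNS-minus-sham response, the error rate is about 5%. ρ and the number of predictors are assumed, and the simulations use single correlation tests, not the covariate-adjusted, L1-penalised or additive models that the SAP mentions.

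Most of this stands. A reader might infer that the plan has adopted the coupled analysis, or that the rates above are this trial's error rates; the documents support neither. A reader might also infer that the artefact would confirm Aim 2 Hypotheses 1 and 3. As written, those hypotheses say only that patients with certain impairments will improve. They state no gradient against better performers; gradient wording appears only in Hypotheses 2 and 4, which concern brain structure. The bias bears instead on Aim 2's general question of response as a function of baseline.

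The reply does not remove two facts. Table 1 names the sham score in writing, and the SAP (dated 1/1/2018) cannot be presumed to override the later protocol (6/30/2021). And the literal SAP rule, regressing memory scores on baseline memory, does not test response even with intake scores. The exploratory label helps only in part, because C6.1 also speaks of testing the Aim 2 hypothesis and C6.2 attaches a power claim.

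**Conclusion.** The point holds as a conditional one. The documents name a predictor that can bias Aim 2 and leave its outcome undefined, so two permitted readings give wrong answers. Under (a), a single unadjusted test falsely rejects about 99% to 22% of the time for assumed ρ of 0.5 to 0.95, at n = 60 with equal variances and no true moderation. FDR control reduces the rate by an amount that depends on the number of predictors, but the estimate stays biased towards greater gain in poorer performers. Under (b), a significant result is close to certain without differential response, provided that the baseline score correlates about 0.5 or more with the session score.

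The Aim 1 comparison is unaffected. Structural predictors are not coupled to the contrast, so the bias in (a) does not reach them. Severity is moderate: the bias depends on analytic choices not yet fixed, and the aim is partly exploratory.

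**What to change.** 1. In Protocol Table 1, delete sham from the predictor cell, so that it refers to baseline cognitive performance from pre-stimulation intake testing.
2. In SAP C6.1, test Aim 2 on the within-subject tVNS-minus-sham contrast adjusted for period or, equivalently, through a treatment-by-predictor term in the mixed model. Use the same definition of response for the structural predictors and in C6.2.
3. State that cognitive predictors come from pre-randomization intake testing, and list the recorded scores.
4. State that the same-test sham score is not used alone as a predictor of that contrast. The two-session mean may serve as a sensitivity analysis only, since it is valid only under equal variances.
5. If any regression of the tVNS score itself is kept, say that a slope below 1 on sham or baseline memory is not read as differential benefit.

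The cost is one table cell and a few SAP sentences, with no new data if intake scores were recorded. The downside is power: intake memory scores are range-restricted by the entry criterion in Protocol C2.4 and come from different tests than the session battery, so cognitive predictors may be somewhat harder to detect. The documents do not allow that loss to be quantified.
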